4.2.3 Safety Endpoints

Safety assessments will include the incidence and severity of reported AEs after randomization, distance visual acuity, slit-lamp biomicroscopy findings, fundus findings, and use of concomitant rescue medications.

5 STUDY ENROLLMENT AND WITHDRAWAL

5.1 Subject Inclusion Criteria

The following are inclusion criteria for a prospective study subject:

1. A male or female subject in good general health, ≥ 22 years of age at the time of the screening visit
2. A patient must be able to read, comprehend and willing to give HIPAA & informed consent.
3. A woman of child-bearing potential must not be pregnant or lactating, must have a negative pregnancy test at screening and must be practicing an adequate method of birth control. Acceptable methods of birth control include intrauterine device (IUD); oral, dermal ("patch"), implant or injected contraceptives; tubal ligation; and barrier methods with spermicide.

4. A subject has the availability, willingness and sufficient cognitive awareness to comply with exam procedures and able to return for all scheduled study visits
5. A subject with a cataract for which routine phacoemulsification extraction and implantation of an intraocular lens has been planned
6. A subject has a preoperative corneal astigmatism of 3.0 D or less in their scheduled operative eye
7. A subject with clear ocular media other than cataract in their scheduled operative eye
8. A subject has the potential for a post-operative Snellen BCDVA of 20/30 or better in their scheduled surgical eye
9. A subject has a lower puncta that can be dilated to 1.0 mm in their scheduled surgical eye.
10. A patient with a dry eye condition being treated with a marketed punctal plug, where the marketed punctal plug will be replaced by a masked study plug.

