3. A woman of child-bearing potential must not be pregnant or lactating, must have a negative pregnancy test at screening and must be practicing an adequate method of birth control. Acceptable methods of birth control include intrauterine device (IUD); oral, dermal ("patch"), implant or injected contraceptives; tubal ligation; and barrier methods with spermicide.
4. A subject has the availability, willingness and sufficient cognitive awareness to comply with exam procedures and able to return for all scheduled study visits
5. A subject with a cataract for which routine phacoemulsification extraction and implantation of an intraocular lens has been planned
6. A subject has a preoperative corneal astigmatism of 3.0 D or less in their scheduled operative eye
7. A subject with clear ocular media other than cataract in their scheduled operative eye
8. A subject has the potential for a post-operative Snellen BCDVA of 20/30 or better in their scheduled surgical eye
9. A subject has a lower puncta that can be dilated to 1.0 mm in their scheduled surgical eye
10. A subject with a dry eye condition being treated with a marketed punctal plug, where the marketed plug will be replaced by a masked study plug.

Study Pre-Operative Exclusion Criteria:

1. A subject with a history of complications, adverse events, trauma or disease in the nasolacrimal area, whether or not it was due to punctal plug wear, including but not limited to dacryocystitis, inflammation or canaliculitis in either eye
2. A subject with structural lid abnormalities (e.g., ectropion, entropion) in their scheduled surgical eye
3. A subject with a puncta >0.9 mm prior to dilation in their scheduled surgical eye
4. A subject experiencing any ocular pain in either eye at the screening visit or on the day the plug is to be inserted
5. A subject with any moderate to severe lid, conjunctival or corneal findings in either eye at the screening visit
6. A subject with any signs of intraocular inflammation (cells/flare) in either eye at the screening visit
7. A subject with a known sensitivity to nepafenac or any inactive ingredient of the punctum plug, silicone, fluorescein, topical anesthetic, or any other products required for study procedures or cataract surgery
8. A subject with a history as a steroid responder
9. A subject with a known or suspected allergy or hypersensitivity to non-steroidal anti-inflammatory drugs (NSAIDs), or to any component of the test article

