5.5.1.3 Reason for Disqualification

A study subject will be disqualified from the study if there was a failure to obtain written informed consent or HIPAA Authorization, improper entry (did not meet all inclusion/exclusion criteria), had a positive pregnancy test (after Visit 1).

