10 STATISTICAL CONSIDERATIONS

10.1 Statistical and Analytical Plans

The primary analysis population will be an ITT (Intent-to-Treat) analysis for all study subjects randomized to treatment that have completed at least one post-operative follow-up visit and had no major protocol violations. Individual study subjects or individual visits may be excluded if a major protocol violation occurs (such as violation of inclusion/exclusion criteria, the use of prohibited medications or non-compliance with protocol requirements that can potentially have significant impact on efficacy).

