A. Evaluation of Biomicroscopy Findings (Lid/Lid Margin, Conjunctiva, Cornea)
 The severity of a sign will be graded by the investigator based on the appearance at each study visit. The following four-point grading scales are to be used to rate Lid/Lid Margin, Conjunctiva, and Corneal findings:

Severity	Score	Description
None	0	Finding is NORMAL
Mild	+1	Finding is FAINT but discernible and diffuse
Moderate	+2	Finding is DISTINCTIVE
Severe	+3	Finding is VERY DISTINCTIVE and dense

B. Evaluation of Anterior Chamber Cells and Flare (Anterior Chamber Cells and Flare)
 The severity of Anterior Chamber Cells and Flare will be graded by the investigator based on the appearance at each study visit. The following five-point grading scales are to be used to rate the following:

i. Anterior Chamber CELLS

Severity	Score	Description
None	0	No cells seen
Trace	+1	1-5 cells seen
Mild	+2	6-15 cells seen
Moderate	+3	16-30 cells seen
Severe	+4	>30 cells seen

ii. Anterior Chamber FLARE

Severity	Score	Description
None	0	No Tyndall effect
Trace	+1	Tyndall effect barely discernible
Mild	+2	Tyndall effect in anterior chamber is clearly visible
Moderate	+3	Tyndall effect in anterior chamber is moderately intense
Severe	+4	Tyndall effect in anterior chamber is very intense. The aqueous humour has a white milky appearance

Appendix 3

GRADING SYSTEMS AND METHODOLOGIES

A. Visual Acuity

Visual acuity will be measured using a Snellen chart both with (BCVA) and without correction (UCVA). The test distance and lighting conditions specified for the investigator's chart must be used and kept constant throughout the study.

B. Fundus Exam

Using an ophthalmoscope, the investigator will examine the back part of the eye (fundus), including the retina, optic disc, choroid and blood vessels. Findings will be recorded as either "Within Normal Limits" or "Abnormal". If findings are abnormal, investigator will rate the findings as either "Not Clinically Significant" or "Clinical Significant". For all Fundus Findings indicated as Clinical Significant the investigator will describe the finding in the appropriate section of the Case Report Form:

C. Cataract Density

Severity	Score	Description
None	0	No cataract
Trace	+1	Early lens opacity
Mild	+2	Intermediate lens opacity
Moderate	+3	Advanced lens opacity
Severe	+4	Hypermaturation lens opacity

D. Ocular Pain Evaluation

Severity	Score	Description
None	0	Absence of pain
Trace	+1	A slight, occasional awareness of an ocular sensation

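### Inclusion criterion 10 is worded as a requirement that every subject be a dry-eye patient wearing a marketed punctal plug, which conflicts with the routine cataract population the trial describes

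*Combined protocol and SAP*

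**What the plan says.** Section 5.1 gives ten numbered inclusion criteria. The tenth is "A patient with a dry eye condition being treated with a marketed punctal plug"; it adds that the study plug takes the place of the marketed one. The synopsis has the same item, and the same addition, with trivial differences in wording: "A subject with a dry eye condition being treated with a marketed punctal plug".

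Four other parts of the protocol act on the list:

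- **Enrolment.** The study population paragraph in the synopsis describes about 75 subjects who have met all the criteria. Section 7.4.1 schedules surgery for a subject who meets all of them.
- **Disqualification.** Section 5.5.1.3 states that a subject will be disqualified for "improper entry (did not meet all inclusion/exclusion criteria"), among other reasons.
- **Replacement.** Section 5.5.2.3 states that a disqualified subject will be replaced.
- **Analysis.** Section 10.1 limits the primary population to randomised subjects with a post-operative visit and no major protocol violation. It gives "violation of inclusion/exclusion criteria" as an example of a major violation and says that subjects or visits may be excluded for it.

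**The concern.** Item 10 has no conditional wording, and it stands in a list in which every item must be satisfied. Taken at its word, it restricts the trial to dry-eye patients who already wear a marketed plug. Nothing else in the protocol describes such a trial.

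The criterion controls who is eligible, who is disqualified, who is replaced and, at the sponsor's discretion, who may be left out of the primary efficacy population. A site, monitor or auditor who applies the text as it stands would classify an ordinary cataract patient as improperly entered. If sites read the item as permission instead, the working eligibility rule differs from the approved one. Whether a given subject is a criteria violation then becomes a matter of interpretation, in a plan where that status can affect the primary set.

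**Working it through.** There is no stated figure to reproduce: section 10.5 says no formal sample size estimation was done, and the point is one of wording. The check sets the relevant text side by side.

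**1. Is item 10 worded as a requirement?** Compare it with item 5 of the same list, which is plainly mandatory: "A subject with a cataract for which routine phacoemulsification extraction and implantation of an intraocular lens has been planned". Items 5 and 10 have the same form, a noun phrase describing the subject. Item 10 contains no *may*, *or*, or *if applicable*. The synopsis repeats it, so it is not a slip in one place.

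**2. Must all items be met?** Yes. The synopsis population paragraph and section 7.4.1 both say so, and section 5.5.1.3 is worded the same way.

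**3. What follows if item 10 is not met?** Section 5.5.1.3 makes disqualification mandatory, and section 5.5.2.3 adds replacement.

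**4. What follows for the analysis?** Less than for eligibility, and the text is not consistent:

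| Section | Treatment of a subject who violated a criterion |
|---|---|
| 10.1 | Primary population defined as having no major violation; such subjects *may* be excluded |
| 10.4.2, ITT set | All subjects with at least one post-operative pain evaluation are kept |
| 10.4.2, PP set | Subjects or visits with significant deviations are removed |
| 10.4.4, safety | All exposed subjects are kept |

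Exclusion from the primary efficacy population is therefore possible under 10.1, but not automatic.

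**5. Does the rest of the protocol describe a dry-eye, plug-wearing population?** No.

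- The title and section 3 refer to cataract surgery and do not mention dry eye.
- Exclusion criterion 1 in section 5.2 covers nasolacrimal history whether or not plug wear caused it, which presumes that some candidates have not worn plugs.
- The Visit 2 procedures in section 7.4.2 list insertion and inspection of the study plug, but no removal of a marketed one. If item 10 applied to everyone, every subject would need that step.

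**6. Size.** With N subjects enrolled and a share p of them satisfying item 10, the number of improper entries under the literal rule is N × (1 − p). N is about 75. The documents give no value or range for p, so no count follows from them. The result is above zero for any p below 1.

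**The case against.** The strongest reply is that nobody would read item 10 as universal. Item 3 of the same list concerns women of child-bearing potential, yet item 1 admits men and women, so the list already contains an item that applies only to a subgroup. The title, objective, exclusion 1 and Visit 2 procedures all point to an allowance, and a sensible site would treat it as one.

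On intent, this stands. It does not rescue the wording. Item 3 names its subgroup and then says what members of it must or must not do. Item 10 only describes a kind of subject, as item 5 does, and imposes no condition that a subject without a plug could be said to satisfy.

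Three stronger readings are tempting, and the documents do not support them.

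- **That anyone failing item 10 is excluded from analysis.** Section 10.1 says such subjects may be excluded, section 10.4.2 keeps those with a post-operative pain evaluation in the ITT set, and section 10.4.4 keeps all exposed subjects for safety. How 10.1 and 10.4.2 fit together is a separate question.
- **That a literal audit would void a particular, large share of the 75 subjects.** Any such number needs an assumed rate of plug wear, and it depends on a reading that the protocol's context contradicts.
- **That, read as permission, item 10 admits dry-eye subjects whose symptoms blur the pain comparison.** The trace grade in Appendix 3 is indeed low: "A slight, occasional awareness of an ocular sensation". But exclusion 4 bars any ocular pain in either eye at screening or on the day of insertion, and exclusion 5 bars moderate to severe lid, conjunctival or corneal findings at screening. What remains is sensation arising after surgery in subjects who were pain-free at entry. Allocation is randomised, and nothing in the documents gives that effect a direction or a size.

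**Conclusion.** The point holds as a contradiction between an operative eligibility rule and the population the trial describes. As written, item 10 makes the ordinary cataract patient an improper entry who is to be disqualified and replaced, and who may be left out of the primary efficacy population. The conclusion rests only on the text of the two lists and of sections 5.5.1.3, 5.5.2.3, 7.4.1 and 10.1; it needs no assumption about how common plug wear is.

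Its practical size is probably small, because the intended meaning can be recovered from context and sites are likely to act on it. It still deserves correction: the protocol attaches a mandatory consequence to failing the criterion, and the correction costs almost nothing. A sensitivity analysis that drops plug wearers is not needed to resolve it.

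**What to change.** In both section 5.1 and the synopsis, take item 10 out of the list of mandatory criteria and state it as an allowance, for example: *Subjects with dry eye treated with a marketed punctal plug may be enrolled if the marketed plug is replaced by the masked study plug.* If the sponsor did mean a requirement, the title, objective and Visit 2 procedures would have to change instead, but nothing in the documents suggests this.

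Optionally, add prior marketed-plug wear by arm to the baseline table in section 10.4.6. The medical history taken at Visit 1 should supply it. The appended nepafenac labels give a modest reason to do so, since they name dry eye syndrome among the ocular surface diseases that may carry increased corneal risk with topical NSAIDs.

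The cost is one sentence in two places, through the amendment process in section 7.1, plus one table row if the option is taken. No visit, measurement or sample size changes.

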5.2 Subject Pre-Operative Exclusion Criteria

The following are pre-surgical exclusion criteria for a prospective study subject:

1. A subject with a history of complications, adverse events, trauma or disease in the nasolacrimal area, whether or not it was due to punctal plug wear, including but not limited to dacryocystitis, inflammation or canaliculitis in either eye
2. A subject with structural lid abnormalities (e.g., ectropion, entropion) in their scheduled surgical eye
3. A subject with a puncta >0.9 mm prior to dilation in their scheduled surgical eye
4. A subject experiencing any ocular pain in either eye at the screening visit or on the day the plug is to be inserted
5. A subject with any moderate to severe lid, conjunctival or corneal findings in either eye at the screening visit
6. A subject with any signs of intraocular inflammation (cells/flare) in either eye at the screening visit
7. A subject with a known sensitivity to nepafenac or any inactive ingredient of the punctum plug, silicone, fluorescein, topical anesthetic, or any other products required for study procedures or cataract surgery
8. A subject with a history as a steroid responder

9. A subject with a known or suspected allergy or hypersensitivity to non-steroidal anti-inflammatory drugs (NSAIDs), or to any component of the test article
10. A subject with only one eye with potentially good vision
11. A subject with a known pathology that may affect visual acuity (as determined by the Investigator); particularly retinal changes that affect vision (macular degeneration, cystoid macular edema, proliferative diabetic retinopathy, etc.) in their scheduled surgical eye
12. A subject that has a condition associated with the fluctuation of hormones that could lead to refractive changes
13. A subject with amblyopia or strabismus
14. A subject with capsule or zonular abnormalities with preoperative lens tilt and/or decentration (e.g., Marfan's syndrome), or may affect postoperative centration or tilt of the lens (e.g. pseudoexfoliation syndrome)
15. A subject has a history of ocular trauma in their scheduled surgical eye
16. A subject that has undergone prior intraocular surgery in the scheduled surgical eye within the last 6 months or laser surgery within three months prior to screening
17. A subject with pupil abnormalities (non-reactive, tonic pupils, abnormally shaped pupils, or pupils that do not dilate at least 3.5 mm under mesopic/scotopic conditions) in their scheduled surgical eye.
18. A subject with a corneal abnormality (e.g., stromal, epithelial or endothelial dystrophies) in their scheduled surgical eye
19. A subject with evidence of clinically significant keratoconus in their scheduled surgical eye
20. A subject with evidence of Epithelial Basement Membrane Dystrophy on slit-lamp exam
21. A subject that has been wearing PMMA lenses within 6 months, gas permeable lenses within one month, or extended-wear or daily soft contact lens within 7 days of their scheduled surgery
22. A subject with an inability to achieve keratometric stability for contact lens wearers
23. A subject with a history of chronic/recurrent inflammatory eye disease (e.g., scleritis, uveitis, herpes keratitis) in either eye
24. A subject with uncontrolled glaucoma
25. A subject that requires an LRI or AI procedure before, during or after cataract surgery

26. A subject that may or is expected to undergo surgical intervention prior to or during the study period other than cataract surgery
27. A subject that requires the use of systemic or ophthalmic NSAIDs or corticosteroid medications during the study period, with the exception of a subject who has been prescribed and has been taking a baby aspirin (≤ 81 mg/daily), (Note: All other NSAIDs or corticosteroid medications must be discontinued at least 48 hours prior to the insertion of the punctal plug)
28. A subject that requires the use of systemic or ocular medications that may affect vision, ocular inflammation or pain
29. A subject with an acute or chronic disease, or illness, that would increase risk or confound study results (e.g., autoimmune disease, connective tissue disease, immunocompromised, suspected glaucoma, glaucomatous changes in the fundus or visual field, ocular inflammation, etc.)
30. A subject with an uncontrolled systemic disease: A potential subject in whom therapy for a systemic disease is not yet stabilized will not be considered for entry into the study
31. A subject with diabetes that is poorly controlled
32. A subject currently participating or has participated in another clinical trial within 30 days prior to enrollment.
33. A subject that requires a stent implant during cataract extraction, with the exception of the implantation of the iStent[®] by GLAUKOS[®].

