Investigator Evaluation of Ocular Pain	1 C	2		4 F	5 F	6 F	7 F
Uncorrected Distance VA	1 C				5	6	7
Manifest Refraction	1 C					6	7
Best-Corrected Distance VA	1 C					6	7
Slit Lamp Examination	1 C			4 F	5 F	6 F	7 F
Insertion of Masked Punctal Plug		2					
Inspection of Masked Punctal Plug		2 D	3 E	4 D	5 D	6 D	7 D
Evaluation of lower puncta	1						
Pupil Measurements			3 G				
Type and Grade Cataract	1						
Monocular Cataract Extraction/IOL Implantation			3				
Fundus Examination	1						7
Removal of Masked Punctal Plug							7 H
Adverse Event Recording		2	3	4	5	6	7

Keys to Abbreviations:

- A = Prior 12 months
- B = Pregnancy test (women of childbearing potential)
- C = Evaluation of Both Eyes
- D = Evaluation using slit-lamp
- E = Visual inspection after surgery
- F = Investigator that performs the slit-lamp and/or ocular pain evaluation
at Visit 4 (Day 1 post-op) should perform ALL post-op visit evaluations
- G = Measurement to occur prior to surgery and immediately after surgery
- H = All masked punctal plugs must be removed at the subject last visit

Visit Schedule:

- v1 = Day -30 to -1
- v2 = 1 to 2 days prior to surgery
- v3 = Surgery Day
- v4 = 1 day post-op
- v5 = 3 ± 1 days post-op
- v6 = 7 ± 1 days post-op
- v7 = 14 ± 2 days post-op

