7.4 Study Visit Schedule

7.4.1 Visit 1: (Screening/Baseline Visit, Day -30 to -1)

A potential study subject qualifications will be assessed according to the inclusion/exclusion criteria listed in the protocol (see [Sections 5.1, 5.2 and 5.3](#)). Prior to undergoing any study-specific procedures, both the study Informed Consent and Authorization for Use/Disclosure of Health Information forms (HIPAA authorization) must be signed by a potential subject who has agreed to participate in the study. During this visit, the following information will be collected/evaluated and recorded in the appropriate sections of the study case report forms for both eyes:

- a. Obtain informed consent and HIPAA release
- b. Record the subject's demographic data and prior 12 month medical history
- c. Record the use of all systemic, topical and/or ophthalmic concomitant medications over the previous 30 days
- d. Urine pregnancy test (if applicable)
- e. Investigator evaluation of ocular pain
- f. Monocular Distance Visual Acuity, Uncorrected and Best-Corrected
- g. Manifest Refraction
- h. Slit-lamp examination
- i. Evaluation of lower punctum (scheduled study eye only)
- j. Type and grade of cataract (scheduled study eye only)
- k. Fundus examination (scheduled study eye only)

A subject who meets all of the study inclusion/exclusion criteria will be scheduled for surgery. Each qualified subject will be scheduled to return to the Investigators office 1 to 2 days before their scheduled surgery for the insertion of the study punctal plug.

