7.4.2 Visit 2: (Masked Punctal Plug Insertion Visit, 1-2 days pre-op)

Each qualified study subject as they are enrolled in to the study will be sequentially assigned an ID number. Treatment assignments for this study have been randomized (see [Section 10.6.1](#) for details on treatment randomization) to determine which one of the two treatments the study subject will receive during the study. In addition, the ID number and the study subject initials will be recorded on study case report forms, in lieu of recording their name, in order to maintain subject confidentiality.

At this visit the following will be performed and recorded:

- a. Investigator evaluation of ocular pain
- b. Insertion of the assigned masked punctal plug in to the lower punctum of the schedule surgical eye
- c. Inspection of the masked punctal plug via the slit lamp to ensure the plug is properly positioned, with the cap still visible and secured in place.

NOTE: The position of the masked punctal plug may be adjusted with forceps

- d. Recording of any reported adverse event(s).
- e. Concomitant medication

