7.4.3 Visit 3: (Surgical Visit, Day 0)

Cataract surgery (e.g., corneal incision, anterior capsulotomy, fragmentation/removal of the lens/cataract) may be performed with the assistance of a femtosecond laser. It is recommended the surgeon use a standard phacoemulsification extraction surgical technique. The anterior capsulotomy should be a well centered continuous curvilinear capsulorhexis approximately 5.5 mm in diameter and the lens must be placed in the capsular bag. A viscoelastic should be used to protect the endothelium. At this visit the following surgical data will be recorded:

- a. Surgical Eye Pupil measurements (prior to and immediately following surgery)
- b. Monocular cataract extraction/IOL implantation recording the following information:
 - Indicate the incision Type (clear cornea, limbal, sclera), Location (nasal, temporal, superior, other) and Size (mm)
 - Nucleus removal time (< 1min, 1 - < 2 min, 2 - < 3 min, 3 - < 4 min, >4 min)
 - Ease of Cortex removal (Very Easy, Easy, Difficult, Very Difficult)
 - Effective Phaco Power (recording of phaco time and power)
 - Type of IOL (e.g., monofocal, toric, etc.) and lens power
 - Record any surgical complications
- c. Visual Inspection of the masked punctal plug at the conclusion of surgery
- d. Subject reported AEs prior to or after surgery
- e. Concomitant medication

Should a surgical complication occur, implantation of the lens will be at the Investigator's discretion. If any of the surgical complications occur, as listed in [Section 5.3](#), the study subject's punctal plug will be removed after surgery and the subject terminated from the study.

Pre-, intra- and post-operative open-label medications will be used as is customary for the Surgeon/Investigator, and should be consistent for all cases. All pre-, intra- and post-operative open-label medications must be recorded on the Concomitant Medication CRF. However the use of any pre-, intra- or post-operative NSAID or corticosteroid is prohibited, with the exception of a subject who has been prescribed and has been taking a baby aspirin (≤ 81 mg/daily). An LRI or AI procedure required for any sphere/cylinder correction before, during or after cataract surgery is prohibited during the study period.

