7.7 Prohibited Medications, Treatments and Procedures

7.7.1 Prohibited Medications

The use of any systemic, topical and/or ophthalmic NSAID or corticosteroid within 48 hours of Visit 2 or during the course of the study (Visit 2 to Visit 7) is not allowed unless medically necessary. If an NSAID, corticosteroid or an immunosuppressant is required for any condition (ocular or systemic), the study subject will be terminated from the study, have their masked punctal plug removed and will be followed through Visit 7 (Day 14) or if required until the condition has resolved or has become medically stable.

Investigational/experimental/off-label usages of drugs or devices are not permitted during the study, except as described in the protocol.

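### Cells/flare and ocular-surface eligibility is checked only at screening, up to 29 days before insertion and possibly on anti-inflammatory drugs, with no graded slit-lamp exam scheduled again until Day 1 post-op

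*Combined protocol and SAP*

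**What the plan says.** **Eligibility (Section 5.2).** Exclusion 6 removes "A subject with any signs of intraocular inflammation (cells/flare) in either eye at the screening visit". Exclusion 5, on moderate to severe lid, conjunctival or corneal findings, is also tied to the screening visit. Exclusion 4 is timed differently: "A subject experiencing any ocular pain in either eye at the screening visit or on the day the plug is to be inserted".

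**Timing.** Section 7.4.1 heads Visit 1 "Screening/Baseline Visit, Day -30 to -1". The visit schedule gives "v2 = 1 to 2 days prior to surgery" for insertion.

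**Washout.** Exclusion 27, which exempts low-dose aspirin, states "All other NSAIDs or corticosteroid medications must be discontinued at least 48 hours prior to the insertion of the punctal plug". Section 7.7.1 matches this: use "within 48 hours of Visit 2 or during the course of the study (Visit 2 to Visit 7) is not allowed unless medically necessary". Neither requires a subject to be off these drugs at Visit 1.

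**Exams before surgery.** Both schedule tables mark the slit-lamp examination at v1, v4, v5, v6 and v7. At Visit 2 the listed slit-lamp task is "Inspection of the masked punctal plug via the slit lamp to ensure the plug is properly positioned". At Visit 3 it is "Visual Inspection of the masked punctal plug at the conclusion of surgery".

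**Text that points the other way.** The synopsis (Study Variables) lists slit lamp with cells and flare for the pre-op and post-op visits without naming visits, although it does name visits for acuity and refraction. Section 11.1 asks for cell and flare values in the source documents at every visit. Appendix 2 says the signs are graded at every study visit.

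**The concern.** The secondary endpoint (Section 4.2.2) is response on summed cells and flare after surgery. Reading those grades as surgical inflammation requires the eye to have been quiet beforehand, and the only scheduled evidence of that is the Visit 1 grade. That grade can be weeks old. It can also have been taken while a drug was suppressing the very signs being screened for, with the drug then withdrawn and no further look scheduled.

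The same gap touches safety. Section 8.2.1 counts a pre-existing condition as an adverse event only if it worsens after study treatment starts, and Section 10.4.4 defines treatment-emergent events as those after insertion. Both need a reference state just before insertion. For lid, conjunctiva and cornea, the scheduled reference may be a month old, and because exclusion 5 admits mild findings that reference is not always zero. Pre-existing cells or flare could also contribute to the grades named in the rescue criteria of Section 7.9.1.

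**Working it through.** The plan states no figure for this point and no sample size calculation (Section 10.5), so there is nothing to reproduce. The checks below are date arithmetic, a comparison of passages, and an illustration under a stated assumption.

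**1. Gap from screening to insertion.** Visit 1 may fall on Day -30 to -1 and Visit 2 on Day -2 or -1.
- Longest gap, insertion on Day -1: -1 - (-30) = 29 days. With insertion on Day -2: -2 - (-30) = 28 days.
- Shortest gap: 0 days.
- Longest gap from the Visit 1 grade to the next scheduled grade (Day 1 post-op): 1 - (-30) = 31 days.
- A subject can be on drug at Visit 1 and still meet the 48-hour rule whenever Visit 1 is at least 2 days before insertion.

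**2. Which text governs Visit 2.** The visit-specific sources agree: both schedule tables, the Visit 2 list (7.4.2) and the Visit 3 list (7.4.3) contain no cell, flare or ocular-surface grading. The three general statements (synopsis, 11.1, Appendix 2) can be read as requiring it. Sites could follow either. Even where a site did grade at Visit 2, exclusions 5 and 6 as worded would not act on the result.

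**3. Weight of one eye.** Planned arms are 50 active and 25 placebo. One eye scored as inflamed only because of pre-existing inflammation moves its arm's rate by 1/25 = 4 points or 1/50 = 2 points.

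**4. Illustration of dilution.** Assume a share q of eyes, equal in both arms, has pre-existing inflammation that does not clear by Day 14. The documents give no value for q. Each arm's clearance rate becomes p(1 - q), and the difference shrinks by the factor (1 - q). For rates p, take the Day 14 clearance figures that Section 2.1 quotes for the 0.3% suspension against vehicle. Two-sided 5% test of two proportions, n = 50 and 25:

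power = Φ[(d - 1.96·SE0)/SE1], where d is the difference, SE0 uses the pooled proportion and SE1 the separate proportions.

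| q | 65% vs 32%: difference | power | 61% vs 24%: difference | power |
|---|---|---|---|---|
| 0 | 33.0 points | 78.5% | 37.0 points | 88.2% |
| 5% | 31.4 | 73.9% | 35.1 | 84.8% |
| 10% | 29.7 | 69.1% | 33.3 | 80.9% |
| 20% | 26.4 | 59.2% | 29.6 | 72.1% |

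**5. Chance imbalance.** The SD of the between-arm difference in prevalence is √[q(1 - q)(1/25 + 1/50)]. At q = 5% this is √(0.0475 × 0.06) = 5.3 points; at 10%, 7.3 points; at 20%, 9.8 points.

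Steps 4 and 5 show sensitivity only. They are not estimates for this trial, and step 4 is pessimistic because it lets none of the affected eyes clear.

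**The case against.** The strongest reply has four parts.

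*The general wording already asks for a grade at Visit 2.* A reader might infer from the schedules that eyes are never re-examined. That is too strong. The eye is at a slit lamp at Visit 2, cells and flare are graded from Day 1, and the synopsis, Section 11.1 and Appendix 2 can be read as including Visit 2. What stands is that the visit-specific instructions omit the grading and the exclusions would not use it.

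*Other exclusions cover most of the risk.* Exclusion 23 removes a history of chronic or recurrent inflammatory eye disease. Exclusion 28 removes subjects who need medication that may affect ocular inflammation. Exclusion 29 names ocular inflammation and is not tied to screening, so an investigator who saw it at Visit 2 would have grounds to exclude. This stands and probably makes prevalence low. It does not supply a scheduled look.

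*There is no systematic bias.* A reader might infer that the treatment comparison is biased. The documents do not support that: assignment is randomized and masked at Visit 2, so pre-existing inflammation is balanced in expectation. Both arms also share the same safety-baseline timing. The primary variable, pain, is rechecked on insertion day. All of this stands.

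*The number of affected eyes is unknown.* If 5-15% of 75 subjects used these drugs at screening, about 4 to 11 eyes (3.75 to 11.25) would be examined on drug. A reader might take that as a count of misclassified eyes. It is not: the percentage is itself an assumption, and an eye examined on drug need not be hiding inflammation. The true number could be zero.

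It can also be said that no planned analysis uses change from the pre-operative cell/flare grade. That is so, but the endpoint still presumes a clear eye at entry.

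**Conclusion.** The gap is real and modest. Exclusions 5 and 6 act only at Visit 1, up to 29 days before insertion and possibly on drug, and no graded exam is scheduled again until Day 1 post-op. The plan rechecks pain on insertion day but not inflammation, and gives no reason for the difference.

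The expected consequence is dilution of the secondary inflammation comparison, chance imbalance with only 25 placebo eyes, and an ocular-surface safety reference that may be a month old. Its size depends on a prevalence the documents do not give. Under the illustrative assumptions, 5% prevalence would cost about 3 to 5 points of power (88.2% to 84.8%, or 78.5% to 73.9%). The true figure could be near zero. The point is worth acting on because the correction is cheap and follows the plan's own treatment of pain; it does not call the trial's main conclusion into question.

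**What to change.** 1. At Visit 2, before a subject number is assigned and before insertion, grade cells, flare, lid, conjunctiva and cornea on the Appendix 2 scales, using the slit lamp already in use. Grade both eyes, because exclusions 5 and 6 apply to either eye.
2. Extend exclusions 5 and 6 to the day of insertion as well as screening, matching exclusion 4. Applying them before number assignment avoids exclusions after randomization.
3. Use the surgical-eye Visit 2 grades as the pre-insertion reference for inflammation and for ocular-surface safety findings.
4. Add the exam to both schedule tables and the Section 7.4.2 list, and reconcile the synopsis, Section 11.1 and Appendix 2 with them so that all say the same thing about which visits carry a cell/flare grade.

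Cost: a few minutes per subject at an existing visit, one added CRF block, and possibly a few more screen failures before randomization.
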